Before smoking the assigned research cigarette, participants will complete a **cigarette purchase task (CPT)**, a behavioral economics-based measure of cigarette reinforcement, which assesses hypothetical demand for cigarettes across a range of prices, and a **cross-price elasticity purchase task**, which assesses hypothetical demand for experimental cigarettes at increasing prices of an individual's preferred brand of cigarettes. Participants will also complete assessment of nicotine withdrawal and craving prior to smoking using the **Minnesota Nicotine Withdrawal Scale (MNWS)**¹⁵ and the **Questionnaire on Smoking Urges**¹⁶. Heart rate and blood pressure will be taken before smoking (some measurements may not be taken if sessions are completed remotely). After smoking, participants will complete assessments of subjective response to smoking with the **modified Cigarette Evaluation Questionnaire (mCEQ)**, the **Duke Sensory Questionnaire (DSQ)**, and the **Nicotine Drug Effects Questionnaire (NDEQ)**. Participants will also complete the MNWS again.

The **Predicted Behavior Questionnaire** will be asked at the beginning of Visits 3 and 4, prior to when the VLNC is smoked. It asks participants to indicate their intentions to use cigarettes and other tobacco products when cigarettes have lower nicotine content and come menthol or non-menthol flavor. The **Expected Utility Questionnaire** will also be administered at Visits 3 and 4, before participants smoke. This questionnaire asks the degree to which participants would use the study cigarettes they just smoked for the past week (menthol or non-menthol) would help them quitting, be less dangerous than smoking, give up tobacco use, smoker fewer cigarettes, etc.

Participants will report their perceptions of the health risks associated with both their usual brand and their study cigarette brand using the **Perceived Health Risks Assessment**.¹⁷

ECOLOGICAL MOMENTARY ASSESSMENT (EMA)

C.5 EMA Procedure. Participants will record cigarette smoking and alternative tobacco use, craving, symptoms of withdrawal, and subjective ratings (e.g., satisfaction, reward, craving reduction, physical sensations like throat hit) associated with smoking the most recent cigarette in response to 2 random prompts to their phone each day. We will use a mobile EMA application, in which participants answer a set of survey questions on their cell phone by selecting

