Patterns of missing data, compliance, distributional properties of variables, and correlations among all measures will be assessed. We will control for potential variables related to missing data and utilize multiple imputation methods (expectation maximization algorithm).¹⁶⁰⁻¹⁶³ Analysis will use linear mixed modeling with random subjects effects^{164,165} to assess the main effect of cigarette type on the primary and secondary outcomes of interest. Models will use a contrast to compare differences between menthol VLNC and non-menthol VLNC at the day-level on predictions of the outcome of interest and that outcome of interest at time t (e.g., morning) predicting behavior (number of cigarettes, any smoking, craving, withdrawal) occurring at a subsequent time point (controlling for cigarette consumption from the previous report). Comparison of usual brand and the menthol VLNC ratings will also be made to determine the perceived similarity of the VLNC to one's own brand. A sub-group of respondents may have fixed (unchanging) ratings of subjective response, craving, cigarettes per day, or withdrawal over the course of 7 days, although this is unlikely given the team's previous research. We will examine baseline and daily factors that set "no changers" apart from those whose show fluctuations in these factors, and examine these as potential covariates in models. Within-person slopes capturing associations between cigarette type and the EMA outcome of interest will be saved in regression models and used to predict the ETM responses.

4. ETM Analyses (Aim 3)

Primary Outcomes: (a) consumption of alternative tobacco products (milligrams of nicotine for alternative tobacco sources) as a function of cigarette type available. Typically, as cigarette price increases, consumption of other tobacco products increases.¹⁴ Secondary Outcomes: (a) breakpoint: the first price at which consumption of the available cigarette is zero; (b) intensity of demand: consumption at the lowest price); (c) elasticity of demand: sensitivity of cigarette consumption to increases in cost, (d) Omax: maximum expenditure for cigarette type available; and (e) Pmax: price at which expenditure is maximized.

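### Lagged EMA models for craving and withdrawal (Aim 2) adjust for previous cigarettes but not for the outcome's own previous value, so a cross-variable lagged slope can arise with no forward effect

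*Combined protocol and SAP*

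**What the plan says.** Section J.3 specifies "linear mixed modeling with random subjects effects" for the main effect of cigarette type. It then describes a day-level contrast of menthol with non-menthol VLNC, covering both the outcome of interest and a lagged model. In the lagged model the predictor is "that outcome of interest at time t (e.g., morning") and the model is "predicting behavior (number of cigarettes, any smoking, craving, withdrawal) occurring at a subsequent time point (controlling for cigarette consumption from the previous report").

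The only lagged covariate named, for all four subsequent outcomes, is the cigarette consumption in that closing bracket. The other adjustments in J.3 are of a different kind. One is "We will control for potential variables related to missing data"; the other concerns factors that distinguish people whose ratings never change. J.3 states no autoregressive term, no residual correlation structure and no centring.

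C.5 (EMA Procedure) shows that the missing covariate is available. At each of two random prompts a day, "Participants will record cigarette smoking and alternative tobacco use, craving, symptoms of withdrawal, and subjective ratings" of the most recent cigarette.

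**The concern.** When the later outcome is number of cigarettes, controlling for previous consumption controls for the outcome's own history. The same is nearly true of any smoking. When the later outcome is craving or withdrawal, that history is left out.

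Suppose satisfaction and craving are correlated within a prompt, and craving carries over to the next prompt. Satisfaction at one prompt is then associated with craving at the next, even if it does nothing to it. Random subject effects remove stable differences between people, not this prompt-to-prompt carry-over. Centring the predictor within person does not remove it either.

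At stake is the reading of any cross-variable lagged slope. The background section on complementary measurements presents EMA as giving causal sequencing of behavior. A slope from satisfaction to later craving could therefore be taken as evidence of temporal order when the model cannot tell it from same-moment association plus persistence.

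**Working it through.** **Plan's own figure.** There is none. The documents give no alpha, effect size, autocorrelation or same-moment correlation for the lagged models.

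**Inputs from the documents.** Analytic n = 100 (J.1, Power). Two prompts a day (C.5). There are 21 EMA days over three 7-day periods, two of them VLNC periods, so 2 × 7 = 14 VLNC days, 28 prompts and 14 morning-to-evening pairs per person.

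**Assumptions.** Two-sided alpha 0.05. Persistence of the outcome from one prompt to the next, φ, between 0 and 0.5. Same-moment within-person correlation of predictor and outcome, r, between 0.1 and 0.5. Correlation of previous cigarettes with each, c = 0.2. Persistence of cigarette count 0.3. No missing prompts. True forward effect zero.

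**Step 1: algebra.** With Y(t+1) = φY(t) + error and standardised variables, the slope of Y(t+1) on X(t), omitting Y(t), is φr. With previous cigarettes in the model, as planned, it is φ(r − c²)/(1 − c²). At φ = r = 0.3:
- without cigarettes: 0.3 × 0.3 = 0.09
- with cigarettes: 0.3 × (0.3 − 0.04)/0.96 = 0.081

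The planned control leaves 0.081/0.09 = 90% of the spurious slope.

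**Step 2: simulation of the slope.** 100 people, 14 morning-to-evening pairs each, random-intercept model, predictors person-mean centred, previous cigarettes included, 400 replicates per row. The Monte Carlo standard error at 5% is √(0.05 × 0.95/400) = 1.1 percentage points.

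| φ | r | Mean slope, planned model | False positives, planned model | False positives, centred previous outcome added |
|---|---|---|---|---|
| 0 | 0.3 | −0.001 | 3.5% | 4.8% |
| 0.1 | 0.1 | 0.006 | 6.0% | 5.8% |
| 0.1 | 0.3 | 0.027 | 14.5% | 6.0% |
| 0.2 | 0.3 | 0.055 | 47% | 4.2% |
| 0.3 | 0.3 | 0.073 | 71% | 5.2% |
| 0.5 | 0.1 | 0.028 | 20% | 3.8% |
| 0.5 | 0.3 | 0.125 | 99% | 4.8% |
| 0.5 | 0.5 | 0.221 | 100% | 3.8% |

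With no persistence there is no bias. Across all 15 combinations run, adding the centred previous outcome gave about 3% to 7%.

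**Step 3: centring.** J.3 uses a random-intercept model and states no centring. In the same simulation, adding the previous outcome uncentred gave mean slopes from about −0.01 to −0.11 and rejection from about 10% to 95%, because a raw lagged outcome is correlated with the random intercept. The covariate helps only if it is centred or handled by an equivalent model.

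**Step 4: menthol versus non-menthol contrast of slopes.** If φ and r are the same under both cigarettes, the spurious slopes are equal and cancel. In simulation, with 14 prompts per condition, the contrast rejected in 4% to 7% of runs. If φ differs, they do not cancel. At φ = 0.3 and 0.5 with r = 0.3, the Step 1 formula gives 0.081 and 0.5 × 0.26/0.96 = 0.135, a difference of 0.054. The contrast then rejected in about 21% of runs. A single lag coefficient shared by both cigarettes cannot absorb that difference, so the lag must interact with cigarette type.

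**The case against.** The strongest reply is that J.3 frames the lagged model inside a menthol versus non-menthol contrast, in counterbalanced order within person. If that contrast is the test, a slope bias common to both cigarettes drops out. This stands, and it limits the point: the near-100% figures describe the lagged slope itself, not the contrast.

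A second reply is that nothing central depends on these models. The Aim 2 hypotheses are differences between cigarette conditions, and the EMA outcomes listed in J.3 include no cross-lagged quantity. This also stands. A reader might infer that the Aim 2 conclusions are invalid, or that the plan will report false forward effects almost every time. The documents support neither. The cigarette-type main effect does not use this adjustment, J.3 speaks only of predicting, and the causal-sequencing remark is general background on EMA. Persistence and correlation are not given, and at low values the error rate is close to nominal.

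A third reply is that the lag is often already present. That is right for number of cigarettes, largely right for any smoking, and right where a variable predicts itself, such as withdrawal predicting later withdrawal. Cross-variable models for craving and withdrawal remain.

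**Conclusion.** The point holds for cross-variable lagged models with craving or withdrawal as the later outcome. For these, the stated control does not stand in for the outcome's own history, and no other section supplies it. The bias exists whenever persistence is non-zero and the predictor and outcome remain correlated within a prompt after allowing for previous cigarettes. Its size is unknown from the documents: under the assumed ranges, false positives for the slope run from about nominal to nearly 100%.

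A contrast of slopes between menthol and non-menthol VLNC is distorted only if persistence or same-moment correlation differs by cigarette type. The 21% figure belongs to one assumed setting and will move with the number of prompt pairs used. The models concerned are supplementary, so this is a worthwhile correction to J.3 rather than a threat to Aim 2.

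**What to change.** In J.3, for lagged models with craving or withdrawal as the outcome:

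- Add the outcome's own value at the previous report, taken within the same 7-day period, alongside previous cigarette consumption.
- Person-mean centre the predictor and the lagged outcome, or use an equivalent dynamic panel model.
- When slopes are contrasted between menthol and non-menthol VLNC, let the lagged outcome interact with cigarette type.

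No change is needed for number of cigarettes, for any smoking, or where the predictor is already the outcome's own lag.

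The cost is a sentence or two in J.3 and one covariate (plus its interaction for contrasts) that is already recorded at every prompt. The first prompt of each period cannot serve as an outcome in any lagged model, so essentially no further data are lost. A lagged outcome with person effects carries a small short-series bias, which was negligible in simulation at 7 to 14 lagged pairs per condition.

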initiate smoking with a menthol cigarette are more likely to report a pleasant first smoking experience;⁴⁹ and this pleasant first smoking experience is associated with increased odds of reporting past 30-day cigarette smoking and past 30-day use of non-cigarette tobacco products.⁴⁹ (3) Literature reviews of tobacco company documents reporting that menthol cigarette marketing campaigns and tobacco companies continue to target consumers, particularly younger ones, with themes of freshness, coolness, crispness and cleanliness,^{22,44,50-52} all positive sensory aspects that were used by YA menthol smokers to describe menthol smoking in a recent qualitative study.^{49,53} and (4) recent evidence showing a rapid increase in menthol cigarette smoking among adult smokers ages 26-34. Thus, we hypothesize that YAs will show higher levels of appeal and reinforcement for menthol vs non-menthol VLNCs, both in the laboratory and via EMA, and appeal/reinforcement for menthol will be linked to purchase behavior on the ETM. Findings from this previous research and our theoretical model provided the foundation for our methodology and design.

A.3. Complementary Measurements of Cigarette Appeal/Reinforcement

Laboratory Assessment – Absolute Appeal/Reinforcement. Laboratory studies provide a great deal of efficiency and internal control, allowing for causal inference of exposure to toxins in tobacco smoke and acute subjective response to smoking as a function of how a cigarette is smoked (e.g., puff volume, duration of smoking, number of puffs), information that cannot be captured through subjective self-report. Assessing cigarette smoking in the laboratory allows for the detailed and precise measurement of a range of puffing behavior (e.g., puff volume, inter-puff-interval) in responses to different cigarette types; product factors on which tobacco companies capitalize.^{22,44,50,54} Previous research shows that smoking behavior in the laboratory predicts changes in plasma nicotine and exhaled CO, and differences in subjective assessments of the tobacco product being measured, including studies of VLNCs.^{44,54-57} These laboratory studies have led to an understanding of the craving reduction and satisfaction differences across menthol and non-menthol cigarettes and the thresholds of menthol and nicotine on subjective responses to cigarette smoking.^{56,58-64}

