The analyses for the aim using ETM data will examine the predictive validity of laboratory and EMA data on the ETM outcomes of interest, separately for each cigarette type. Hierarchical linear regression models will predict the ETM outcome of interest, controlling for baseline cigarettes per day, nicotine dependence, other tobacco use, and relevant demographics in Step 1 and then

including the laboratory or EMA-derived slopes of appeal/reinforcement in Step 2. Models will separately examine the effects of laboratory and EMA measurements of appeal/reinforcement on the ETM outcomes of interest.

5. Exploratory Analyses

Differences by age (18-24 vs 25-34), sex, race/ethnicity, alternative tobacco product use, and ETM flavor and product preference. Menthol cigarettes are disproportionately used by women, as well as Black and Hispanic smokers.^{18,166-168} As such, sex and race/ethnicity will be examined as moderators of outcomes, as sample size permits. This allows us to adhere to NIH guidance examining sex as a biological variable. Variation in the use of alternative tobacco products during each 7-day take-home phase will be examined as a possible moderator of the reinforcing effects of the research cigarette to which participants are assigned, as well as an outcome assessment of compensatory tobacco use. Given the popularity of menthol cigarette use in adults aged 26-34 years and alternative tobacco product use in this age group,^{17,169-171} flavor preference by product type (e-cigarettes, little cigars) will be examined as an exploratory outcome from the ETM analyses.

Laboratory and EMA concordance and predictive utility. We will examine the association of laboratory and EMA measurements of appeal/reinforcement and determine whether correlations between these measures differ in magnitude by menthol vs non-menthol use and by VLNC vs usual brand. A weak or non-significant correlation could indicate that these paradigms tap into different dimensions of reinforcement/appeal. We will also compare the utility of laboratory vs EMA outcomes as predictors of ETM outcomes to determine the relative contribution of each measurement paradigm. This would advance theoretical models and facilitate future research by identifying the most relevant aspects of abuse liability that uniquely account for the role of menthol in increasing risk for dependence.

6. Study Timeline.

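### The ETM regressions use a slope across cigarette types as the appeal predictor, and no named term carries the person's rating of the cigarette on sale

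*Combined protocol and SAP*

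**What the plan says.** Section J.3 (EMA Analyses, Aim 2) defines the predictor: "Within-person slopes capturing associations between cigarette type and the EMA outcome of interest will be saved in regression models". The saved slopes then serve as predictors of the ETM responses.

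Section J.4 (ETM Analyses, Aim 3) sets out the regressions. They examine the predictive validity of the laboratory and EMA data "on the ETM outcomes of interest, separately for each cigarette type". Step 1 is described as "controlling for baseline cigarettes per day, nicotine dependence, other tobacco use, and relevant demographics in Step 1". Step 2 is described as "including the laboratory or EMA-derived slopes of appeal/reinforcement in Step 2". The primary ETM outcome is consumption of alternative tobacco products. The five cigarette demand indices (breakpoint, intensity, elasticity, Omax, Pmax) are secondary.

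Section J.2 (Laboratory Analyses, Aim 1) also defines its primary appeal measure, relative reinforcing value, as a within-subject difference in ratings between cigarettes.

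Section C.6 describes the two markets. In ETM 1 the non-menthol VLNC is the only cigarette sold. In ETM 2 the menthol VLNC is sold at rising prices with the non-menthol VLNC also available.

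The hypothesis in section B (Conceptual Framework) is that "appeal/reinforcement for menthol will be linked to purchase behavior on the ETM".

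**The concern.** The regressions are meant to show whether the appeal of a cigarette predicts what people buy. The predictor named for this is a contrast between cigarettes, while the models are split "separately for each cigarette type". How much a person liked the cigarette on sale is collected, both in the laboratory and by EMA, but it is not named in Step 1 or Step 2.

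This is the only regression described for Aim 3. If liking of the non-menthol VLNC drives demand for it in ETM 1, a contrast can miss much of that link. A null coefficient would then be hard to interpret: it could mean that appeal does not predict purchasing, or that the predictor did not measure the relevant appeal. J.3 and J.4 also do not say which contrast the slope is, so two analysts could construct different predictors from the same text.

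**Working it through.** **1. Terms in the model.** Step 1 has baseline cigarettes per day, dependence, other tobacco use and demographics. Step 2 has slopes. None of these is the rating of the cigarette on sale.

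**2. Same slope, different liking.** On an arbitrary scale, person A rates the menthol VLNC 6 and the non-menthol VLNC 5, and person B rates them 2 and 1. The contrast is 6 - 5 = 1 for A and 2 - 1 = 1 for B. The ETM 1 model gives both the same predictor value although they differ by 4 points on the cigarette being sold.

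**3. Share of R-squared kept when only the level matters.** The documents give no correlation, variance or R-squared for this analysis, so there is no stated figure to reproduce and the inputs here are assumptions. Let S be the rating of the cigarette on sale, O the rating of the comparison cigarette, rho their between-person correlation and k = SD(O)/SD(S). If demand depends on the ratings only through S, the contrast keeps the squared correlation between S and S - O:

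share = (1 - rho·k)² / (1 + k² - 2·rho·k), which is (1 - rho)/2 when k = 1.

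| rho (k = 1) | 0 | 0.2 | 0.4 | 0.6 | 0.8 | 0.9 |
|---|---|---|---|---|---|---|
| share kept | 50% | 40% | 30% | 20% | 10% | 5% |

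Unequal SDs at rho = 0.6:
- k = 0.5: 0.49/0.65 = 75%
- k = 1.5: 0.01/1.45 = 0.7%, about 1%

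A simulation with 14 EMA prompts per condition (residual variance assumed equal to between-person variance, k = 1) gave 40%, 29%, 19% and 8% at rho 0.2, 0.4, 0.6 and 0.8. If Step 1 covariates absorb 10% to 50% of the shared level, the share at rho 0.4 to 0.8 becomes about 11% to 38%.

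**4. ETM 2, where both VLNCs are sold.** Suppose demand for the menthol VLNC depends on S - c·O, with k = 1. Then share = (1 + c)²(1 - rho) / [2(1 + c² - 2c·rho)].

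| c (rho = 0.6) | 0 | 0.25 | 0.5 | 0.75 | 1 |
|---|---|---|---|---|---|
| share kept | 20% | 41% | 69% | 93% | 100% |

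**5. Illustrative power.** Assume two-sided alpha 0.05 and seven predictors in total, and test one added term with the noncentral F. At n = 100 (section J.1), a level effect with R-squared 0.074 has 80% power.

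| share kept | 100% | 50% | 30% | 10% |
|---|---|---|---|---|
| n = 100 | 80% | 49% | 32% | 14% |
| n = 138 (section C.4) | 91% | 63% | 42% | 17% |

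**6. Cost of entering level and contrast together.** With k = 1, the squared correlation between them is (1 - rho)/2, so the variance inflation factor is 1/[1 - (1 - rho)/2] = 2/(1 + rho). This gives 1.43, 1.25 and 1.11 at rho 0.4, 0.6 and 0.8. Standard errors grow by the square root: about 20%, 12% and 5%. A joint two-degree-of-freedom test of the same R-squared 0.074 (eight predictors) has 70% power at n = 100 and 85% at n = 138.

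**The case against.** The strongest defence is that a difference is what the investigators intend. Section A.3 presents the ETM as a measure of relative appeal, and J.2 defines reinforcing value as a within-subject difference. The primary Aim 3 outcome is alternative-product consumption. Relative preference for menthol is a plausible predictor of switching when menthol cigarettes are unavailable. This stands, and it is why the slope should be kept. It does not explain why the level is left out, particularly for demand in ETM 1.

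A second defence is that the slope may mean each VLNC against usual brand, which would be specific to a cigarette type and fit the by-type models. A reader might infer that no slope can exist within one type, but this reading shows that the text does not force that conclusion. The predictor would still be a difference, and the formula in step 3 applies with the corresponding rho and k.

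Third, the Step 2 wording could mean laboratory measures as such, with slopes coming only from EMA, and the sentence after it speaks of measurements generally. The laboratory models might then carry type-specific ratings. The text does not settle this.

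Two further inferences are not supported. One is that the menthol rating vanishes because the three types are scored 1, 2, 3; the plan gives no such scoring and treats type as categories. The other is that the slope's sign is reversed in ETM 1; the sign depends only on which cigarette is the reference.

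**Conclusion.** The point holds as a gap in the model specification. The named Step 2 predictor is a difference between cigarettes, the contrast is not defined, and no named term carries the rating of the cigarette on sale. It matters most for the secondary demand indices in ETM 1.

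A reader might conclude that the analysis keeps only 10% to 30% of the explained variance. The documents do not support a fixed figure. That range requires rho between 0.4 and 0.8, equal SDs, and demand driven only by the rating of the cigarette on sale. Under other assumptions the share runs from near 0% to 100%, and the high end is plausible in ETM 2. The calculations concern cigarette demand and do not quantify any loss for the primary outcome, alternative-product consumption. The power figures also depend on n: the low values at n = 100 improve at 138, although the loss relative to the level remains.

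This is an inexpensive improvement to an analysis that would otherwise be hard to interpret if null. It does not invalidate Aim 3.

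**What to change.** In J.3 and J.4:

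- Define the slope as the menthol versus non-menthol VLNC contrast.
- For ETM 1, enter in Step 2 the person's rating of the non-menthol VLNC (the laboratory rating, or the mean over the EMA week) together with that contrast.
- For ETM 2, enter the menthol and non-menthol VLNC ratings together. This is equivalent to entering their mean and difference, so the relative measure is kept.
- State that the laboratory models use the same construction.

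The cost is wording and one extra degree of freedom per model, with no new data. The slope coefficient loses some precision because it is correlated with the level (step 6: standard errors about 5% to 20% larger at rho 0.8 to 0.4 with equal SDs).
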